13.1 Adverse Events

In accordance with 21 Code of Federal Regulation (CFR) 312.32(b) and International Conference on Harmonisation (ICH) Guidance E2A, an adverse event is any untoward medical occurrence in a clinical investigation of a patient administered a pharmaceutical product and that does not necessarily have a causal relationship with the treatment. An AE is therefore any unfavorable and unintended sign (including an abnormal laboratory finding), symptom, or disease temporally associated with the administration of an investigational product, whether or not related to that investigational product. An unexpected AE is one of a type not identified in nature, severity, or frequency in the current Investigator's Brochure or of greater severity or frequency than expected based on the information in the Investigator's Brochure.

Examples of an AE include:

- Significant worsening or exacerbation of underlying medical condition.
- Significant abnormal findings from physical examinations, vital signs or laboratory tests.

The following examples are not considered AE:

- Medical or surgical procedure, although the condition leading to the procedure is usually an AE.
- Anticipated day-to-day fluctuations of preexisting medical conditions (including laboratory values) as long as worsening from baseline does not occur.
- Signs or symptoms of the disorder being studied unless they become more severe or occur with a greater frequency than occurring at baseline.
- Normal progression of the disorder being studied unless it is more severe or occurs with greater speed/frequency than expected.

All AE, whether elicited by questions from study staff, volunteered, or noted on physical examination/laboratory testing, and regardless of causality or severity, will be assessed and recorded in the eCRF beginning after the first administration of study drug and ending on Extension Day 561 or 84 (± 3) days after last dose of study drug if ET.

The assessment of an AE will be done pursuant to definitions set forth by ICH Good Clinical Practice (GCP) guidelines and applicable regulatory requirements.

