---------------------------	--

Objective	The objective of the study is to generate open-label, longer-term safety, tolerability, and efficacy follow-up data in patients with EG and/or EoD who completed Study AK002-016 or Study AK002-012. This study also provides patients randomized to placebo in Study AK002-016 the option to receive active dosing.
Safety Endpoints	The safety and tolerability of AK002 will be assessed by determining the incidence, relationship to study drug, and severity of TEAE, withdrawals due to adverse events, vital signs, laboratory tests, changes in concomitant medication use due to adverse events, immunogenicity, and other safety parameters.
Pharmacodynamic/ Efficacy Endpoints	
 • Short-Form Health and Well Being Survey (SF-36) questionnaire • Gastrointestinal symptomatology (EG/EoD PRO questionnaire) • Change in blood eosinophil count • Change in eosinophil counts in gastric and/or duodenal biopsies
Study Population	
Patients who complete Study AK002-016 or Study AK002-012 will have the option to receive AK002 in an open-label manner.
 
A patient is categorized as having completed Study AK002-016 if 6 infusions of study drug are administered and the patient is followed at least through the Day 176 visit for AK002-016. Patients are followed under the AK002-016 study until they receive their first dose in the AK002-016X study.
 
A patient is categorized as having completed Study AK002-012 if the patient received all cohort-appropriate doses and was followed for 5 months after the last dose of study drug in AK002-012.

Patient Selection Criteria	
Inclusion Criteria
 
Patients are eligible for the study if all of the following criteria are met:
 
 1) Provide written informed consent. 2) Completed Study AK002-016, defined as having received 6 infusions of study drug and followed through at least Day 176 (± 3 days) or completed Study AK002-012, defined as having received the cohort-appropriate number of doses and followed for 5 months after last dose of study drug. 3) If patient is on preexisting dietary restrictions, willingness to maintain those restrictions until the seventh dose has been received. After the seventh dose, diet may be liberalized. 4) Able and willing to comply with all study procedures.

Patient Selection Criteria cont.	Inclusion Criteria cont.

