- 8) The PRO should be completed by the patient, around the same time each day using ViedocME electronic portal. Patients with concomitant history of asthma and/or atopic dermatitis symptoms will receive an extra question about each, as appropriate. If the dysphagia question was populated in AK002-016, it will continue to populate in the daily ViedocME questions for AK002-016X. The PRO may be completed via paper if electronic access is not possible.
- 9) Completed in clinic by the patient (complete prior to blood draw, physical examination, or vital sign measurements) during study visits, using ViedocME electronic portal. May be completed via paper if electronic access is not possible.
- 10) A small amount of urine collected for urinalysis will be used for dipstick pregnancy test (for women of childbearing ability) predose on all infusion days and on Day 512 (± 3) or 35 (± 3) days after last dose if ET. Test kits will be supplied by the central laboratory. Tests will be completed on site and evaluated prior to infusion.
- 11) Endpoint IRT to be used to assign kit numbers for each patient dosing. Current patient body weight (taken day before infusion or day of infusion) will be entered into IRT and amount of AK002 to be mixed with 0.9% NaCl will be calculated via Endpoint.
- 12) All patients will self-administer 80 mg oral prednisone 12–24 hours prior to the first infusion. An approved alternative(s) may be used with the approval of the Medical Monitor. Premedication may be administered prior to subsequent infusions at the Investigator's discretion, but only with written approval from the Medical Monitor.
- 13) Study drug will be administered as a single peripheral IV infusion over at least a 4-hour period for Dose 1. Second and subsequent infusions can be given over at least a 2-hour period, depending on prior infusion tolerability. After the sixth infusion a 1-hour infusion schedule may be used. Refer to the Pharmacy Manual.
- 14) Specimen processed by central laboratory. See central laboratory manual for collection and processing details.
- 15) Blood for CBC with differential, including absolute blood eosinophil count, will be obtained just prior to each infusion, 1 hour (± 15 minutes) after the end of each infusion as well as on Extension Days 512, 533, and 561 (± 3 days) or 35, 56, and 84 (± 3) days after last dose of study drug if ET.

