- 16) Blood for Chemistry will be obtained just prior to each infusion as well as on Extension Days 512, 533, and 561 (± 3) or 35, 56, and 84 (± 3) days after last dose of study drug if ET.
- 17) Urine for Urinalysis will be collected on Extension Days 1, 197 (± 3), and 512 (± 3) or 35 (± 3) days after last dose of study drug if ET.

Table Notes cont.

- 18) Blood for PK will be collected on Extension Days 1, 197 (± 3), and 512 (± 3) or 35 (± 3) days after last dose of study drug if ET.
- 19) Blood for ADA will be collected on Extension Days 1, 197 (± 3), and 512 (± 3) or 35 (± 3) days after last dose of study drug if ET. ADA will also be collected when an immunogenicity-related AE occurs.
- 20) Blood for Total Serum IgE will be collected on Extension Day 1 and Extension Day 512 (± 3) or 35 (± 3) days after last dose of study drug if ET.
- 21) The consent form for AK002-016X must be signed *prior* to the patient taking prednisone premedication for the AK002-016X study.
- 22) The final EGD and Day 176 hematology assessment (first safety follow-up) for AK002-016 *must* be collected *prior* to the patient taking prednisone premedication for AK002-016X. Therefore, dosing in AK002-016X must take place at least 1 day after completion of the Day 176 visit for AK002-016.
- 23) See [Appendix 6](#) for biopsy assessments. EGD should occur on Day 211 (± 3) and Day 505 (± 3) or 28 (± 3) days after last dose of study drug if the patient discontinues the study early and agrees to have an early termination biopsy.
- 24) Non-serious AE will be captured from Day 1 (first dose of study drug) through Day 561 (± 3) or 84 (± 3) days after last dose of study drug if ET.
- 25) Adverse events of special interest will be captured from Day 1 (first dose of study drug) through Day 561 (± 3) or 84 (± 3) days after last dose of study drug if ET.
- 26) Serious adverse events will be captured from Day 1 (first dose of study drug) through Day 561 (± 3) or 84 (± 3) days after last dose of study drug if ET.

6. Criteria for Evaluation

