11.4.10 COVID-19 Testing

Testing for COVID-19 is not required for this study but may be implemented by the study site at any time during the study due to safety regulations or procedures. Testing for COVID-19 may be individually mandated by EGD facilities and, if this is required, will be consented through the site and not listed in the AK002-016X informed consent form (ICF).

12. Evaluations and Procedures by Visit

Written, informed consent will be obtained before any study procedure is performed.

General Information:

- Evaluations and procedures by visit are shown in [Table 1](#).
- All recorded clock times should utilize a 24-hour clock.
- Extension Day 1 is the day of the first infusion in this extension study.

12.1 Prior to Extension Day 1

The following procedures will be performed prior to Extension Day 1:

- Obtain written informed consent ***prior*** to patient receiving premedication.
- Verify eligibility for the study.
- Patient to self-administer 80 mg oral prednisone (or approved alternative) 12–24 hours prior to predicted infusion start.

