13.2 Serious Adverse Events

A SAE is defined as an AE that meets 1 of the following criteria:

- Death
- A life-threatening adverse event that places the patient at risk of death at the time of the event. It does not refer to an event that hypothetically might cause death if it were more severe.
- Inpatient hospitalization or prolongation of existing hospitalization.
- A persistent or significant disability/incapacity.
- A congenital anomaly/birth defect occurring in the offspring of a study patient.
- Other important medical events may also be considered a SAE when, based on appropriate medical judgment, they jeopardize the patient or require intervention to prevent one of the outcomes listed above.

The date that an AE meets 1 of the criteria listed above is the date that it becomes an SAE. Conversely, the date that the SAE no longer meets 1 of the criteria listed above is the end date of the SAE. A new AE with an outcome of “recovering” may be created to address the ongoing AE once it is no longer considered serious.

Serious adverse events will be assessed and recorded after the first administration of study drug and ending on Extension Day 561 (± 3) or 84 (± 3) days after last dose of study drug if ET.

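### AE, SAE and AESI recording opens only at the first AK002 infusion, 12–24 hours after a protocol-mandated prednisone dose, and no study is named as owner of that interval for AK002-012 entrants

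*Combined protocol and SAP*

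**What the plan says.** **Start of recording.** Section 13.1 has AEs recorded "beginning after the first administration of study drug and ending on Extension Day 561" (or 84 days after the last dose for early terminators). Section 13.2 says "Serious adverse events will be assessed and recorded after the first administration of study drug". The synopsis (Safety Evaluations), Table 1 notes 24–26, and Sections 13.3, 13.7.1 and 13.7.4 use the same start, with small differences between at and after the first dose.

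**Premedication.** Table 1 note 12 says "All patients will self-administer 80 mg oral prednisone 12–24 hours prior to the first infusion", and Section 12.1 allows an approved alternative. Section 12.1 also instructs sites: "Obtain written informed consent *prior* to patient receiving premedication". Table 1 note 21 repeats that order for the AK002-016X consent form. Section 12.1 lists consent, eligibility and prednisone; it lists no AE collection.

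**Who follows the patient before the first dose.** For one parent study the synopsis (Study Population) is explicit: "Patients are followed under the AK002-016 study until they receive their first dose in the AK002-016X study". The synopsis Study Design and Section 5.1 agree. AK002-012 counts as complete after 5 months of follow-up from its last dose, and nothing extends that follow-up to the first extension dose.

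**Who counts.** Enrollment is the first open-label AK002 dose (Section 10.1). The Safety population is everyone who received study medication (Section 15.2).

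**The concern.** The prednisone belongs to this protocol: AK002-016X mandates it, and it is taken only after AK002-016X consent. Section 13.1 asks for AEs whatever their cause, and Section 13.6.4 asks about causality to study procedures, yet recording opens only after the first post-consent intervention has been given. In a study whose stated objective is longer-term safety and tolerability, a site that follows Sections 13.1 and 13.2 literally could leave out a harm from a step the protocol itself requires. For AK002-012 entrants, the protocol names no other study to pick it up.

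**Working it through.** The protocol gives no figure for this interval, so there is none to reproduce. The check sets the rules side by side for an event that begins between prednisone and the first infusion.

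**1. Where each event goes**

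| Event | AK002-016 entrant | AK002-012 entrant |
|---|---|---|
| Starts and resolves before infusion | Parent study owns the period; if significant, also medical history here (Table 1 note 1) | No assigned AE record: not ongoing, and not an event of the completed parent study |
| Starts before infusion, still ongoing | Parent study; medical history here | Medical history here, but not as an AE, so the severity and causality grading of 13.6 does not apply |
| Starts before, worsens after infusion | TEAE here (15.5) | TEAE here (15.5) |
| Starts after infusion | AE here (13.1) | AE here (13.1) |
| Reacts, never infused | Stays under parent study; not enrolled here, not in Safety population | No owner named; not enrolled, not in Safety population |

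The gap is therefore the first and last rows of the right-hand column, plus the loss of AE status in the second row.

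**2. Conflicting text.** Section 12.2 has AEs, including SAEs and AESIs, documented throughout the Day 1 clinic visit, with no exception for the time before the infusion. Section 13.7.2 requires reporting of any SAE during the study, whatever its attribution. Read broadly, these reach pre-infusion Day 1 visit events and SAEs. Sections 13.1 and 13.2 exclude both. Because Section 10.1 ties enrollment to the first dose, it is also unclear whether the prednisone interval is during the study at all.

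**3. The TEAE definition.** Section 15.5 uses the start date of the first infusion, not its time. If the infusion begins h hours after midnight (h up to 12), then h of the 12–24 hours since prednisone fall on Day 1. An event in those h hours, if recorded, would count as treatment-emergent although it preceded any AK002 in this study. Simply opening capture earlier would therefore put pre-infusion events into the TEAE tables.

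**4. Scale.** Inputs: 12–24 hours (Table 1 note 12) and a ceiling of about 183 patients (Section 15.1).
- Time at issue if all 183 enroll: 183 × 12/24 = 91.5 to 183 × 24/24 = 183 patient-days.
- Expected events starting in the interval = 183 × p; chance of at least one = 1 − (1 − p)^183. The protocol gives no p, so these rates are assumptions:

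| Assumed p per patient | Expected events | Chance of at least one |
|---|---|---|
| 0.1% | 0.18 | 16.7% |
| 0.5% | 0.92 | 60.0% |
| 1% | 1.83 | 84.1% |
| 5% | 9.15 | about 100% |

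These are ceilings over all entrants, not estimates of lost events. The number is said to be based on AK002-016 enrollment, and those patients have a named owner for the interval. For the unowned group the expected count is m × p, where m, the number of AK002-012 entrants, is not given.

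**The case against.** The case against is substantial, and much of it limits the point.

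- **A reader might infer that these events are recorded nowhere.** The protocol does not support that. Events starting after the infusion are recorded whatever their cause, worsening events become TEAEs, ongoing ones enter medical history, and Sections 12.2 and 13.7.2 can be read to reach further. Drugs used to treat a reaction would also leave a trace: medications within 30 days before Day 1 are recorded (Table 1 note 2), with indication (Section 11.3.1).
- **A reader might infer that AK002-016 entrants' events land in the wrong study and contaminate blinded data.** Assignment to the parent study is an explicit, repeated rule. Table 1 note 22 requires the final EGD and Day 176 hematology to precede prednisone, so those assessments are protected. The continued blinding described here concerns differential cell counts, and AK002-016's own AE rules are not in this text.
- **A reader might infer that no study captures AK002-012 entrants.** That depends on when AK002-012 closes its AE and SAE collection, which this protocol does not say. The supportable statement is that AK002-016X names no owner.
- **Starting at first study drug is a consistent choice**, repeated across sections, and the interval is short.

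What stands after all this: an AK002-012 entrant's event that starts and resolves before infusion has no assigned AE record, patients who are never infused drop out of view here, and the capture rules disagree. Medical history and medication logs do not replace an AE record with severity, causality and expedited reporting.

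**Conclusion.** The point holds in a narrow form. For AK002-012 entrants, the protocol leaves 12–24 hours after a mandated premedication without an assigned owner for AE recording. For all entrants, Sections 12.2 and 13.7.2 need reconciling with 13.1 and 13.2. Its size in events cannot be stated, because neither the number of AK002-012 entrants nor an event rate is given; the calculated ceilings rest wholly on assumed rates. The conclusion assumes that study medication in Section 15.2 means AK002, as the wording of Section 15.5 suggests. It does not extend to saying that such events go unrecorded in every patient, or that parent-study data are compromised. This is a minor completeness issue in the safety record; it affects no test or sample size.

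**What to change.** - Start AE capture in AK002-016X at premedication and SAE capture at consent, including for consented patients who are never infused.
- Align the synopsis, Table 1 notes 24–26 and Sections 13.1, 13.2, 13.3, 13.7.1 and 13.7.4 with Sections 12.2 and 13.7.2.
- State, separately for AK002-016 and AK002-012 entrants, which study owns the interval from consent to first infusion.
- Record onset time as well as date. Define TEAE in Section 15.5 by infusion start date and time, and carry this into the separate analysis plan that Section 15 announces. Without this change, pre-infusion events on Day 1 would be counted as treatment-emergent.
- List pre-infusion events separately, including those in patients outside the Safety population.

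Cost: wording changes, an onset-time field and a few extra pre-infusion records. Dosing, premedication and visit timing are untouched. Label: cheap improvement.

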13.2 Serious Adverse Events

A SAE is defined as an AE that meets 1 of the following criteria:

- Death
- A life-threatening adverse event that places the patient at risk of death at the time of the event. It does not refer to an event that hypothetically might cause death if it were more severe.
- Inpatient hospitalization or prolongation of existing hospitalization.
- A persistent or significant disability/incapacity.
- A congenital anomaly/birth defect occurring in the offspring of a study patient.
- Other important medical events may also be considered a SAE when, based on appropriate medical judgment, they jeopardize the patient or require intervention to prevent one of the outcomes listed above.

The date that an AE meets 1 of the criteria listed above is the date that it becomes an SAE. Conversely, the date that the SAE no longer meets 1 of the criteria listed above is the end date of the SAE. A new AE with an outcome of “recovering” may be created to address the ongoing AE once it is no longer considered serious.

Serious adverse events will be assessed and recorded after the first administration of study drug and ending on Extension Day 561 (± 3) or 84 (± 3) days after last dose of study drug if ET.

13.3 Adverse Events of Special Interest

Adverse events of special interest for this study include:

- Malignancies confirmed by histopathological report. Mast cells and eosinophils are part of the normal immune response and by decreasing their function, AK002 could theoretically increase the risk of malignancy.
- Parasitic infections confirmed by positive clinical laboratory test. Eosinophils are especially active in protecting the body from parasitic infections and decreasing their function could theoretically increase the risk of parasitic and opportunistic infections.
- Opportunistic infections (infections known to be more severe or occur more frequently in immunosuppressed populations) as confirmed by positive clinical laboratory test.
- Infusion-related reactions and hypersensitivity reactions, including anaphylaxis.

Adverse events of special interest will be assessed beginning after the first administration of study drug and ending on Extension Day 561 (± 3) or 84 (± 3) days after last dose of study drug if ET. Any new AESI must be recorded in the Adverse Event eCRF and designated as an “adverse event of special interest.” If new information related to any previously reported AESI is identified, the appropriate eCRF should be updated.

13.4 Infusion-Related Reactions

All AE considered by the Investigator *to be related to the infusion* of the biological substance and occurring within 24 hours of the start of the study drug infusion, should be captured as 1 AE, termed “Infusion-Related Reaction” (IRR).

Common symptoms of IRR include:

• Flushing	• Nausea
• Chills	• Vomiting
• Back or abdominal pain	• Sweating
• Chest discomfort or tightness	• Fever
• Dizziness	• Urticaria
• Shortness of breath	• Pruritus
• Headache	• Bronchospasm
• Hypotension or hypertension	

All symptoms experienced by a patient during an IRR will be listed in the eCRF under 1 IRR, unless the Investigator believes a symptom is not part of the IRR, in which case it will be recorded separately. The start time of the IRR will be captured as the start time of the first symptom, and the end time of the IRR will be captured as the end time of the last symptom.

Any medications used within 24 hours of an infusion for the treatment of an IRR are not considered prohibited medications nor deviations from the protocol.

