13.5 Anaphylaxis

A suspicion of anaphylaxis will be carefully monitored and treated according to standard of care. Emergency crash cart equipment and medications, including multiple doses of epinephrine, vasopressors, and bronchodilators, will be available at all times during the conduct of the study. To define anaphylactic reactions in a consistent and objective manner, all events of suspected anaphylaxis will be evaluated using Sampson's Criteria for Anaphylaxis ([Appendix 7](#)). The assessment of an AE will be done pursuant to definitions set forth by ICH Good Clinical Practice (GCP) guidelines and applicable regulatory requirements.

If a patient experiences signs or symptoms of anaphylaxis, the patient may be treated with standard of care, such as diphenhydramine, acetaminophen, methylprednisolone, epinephrine, and other supportive measures along with cessation of the infusion.

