15.5 Analysis of Safety Endpoints

Adverse Events: All AE will be coded using the Medical Dictionary for Regulatory Activities (MedDRA) and will be classified by MedDRA system organ class and preferred term. Listings will include all AE collected on study. The summaries of AE will be based on TEAE, defined as an AE reported in the clinical database with a date of onset (or worsening) on or after the start date of the first intravenous infusion of the study medication.

Patient incidence (N and %) of TEAE will be summarized as follows:

- Overview of TEAE to include
 - Number (%) of patients who report at least one TEAE overall, by severity and by relationship
 - Number (%) of patients who report at least one serious TEAE
 - Number (%) of patients who report at least one TEAE leading to treatment discontinuation
 - Number (%) of patients who report at least one TEAE of special interest
- TEAE by preferred term
- TEAE by system organ class and preferred term

- TEAE by maximum severity, system organ class, and preferred term
- Drug-related TEAE by system organ class and preferred term
- TEAE leading to withdrawal by system organ class and preferred term
- Serious TEAE by system organ class and preferred term
- TEAE of special interest by system organ class and preferred term

Clinical Laboratory Assessments: Samples will be obtained for the clinical laboratory tests identified in Section 11.4, and laboratory tests to be summarized include blood chemistry, hematology, urinalysis, and ADA.

Descriptive statistics will be used to summarize laboratory results at baseline, each visit, and the change from baseline for each visit. In addition, shift tables will summarize the laboratory results relative to normal reference ranges at baseline and each post-baseline time point.

Vital Signs: Vital signs will be summarized at baseline, each visit, and change from baseline at each visit.

Physical Examination: New or worsening symptoms in the symptom-directed physical examinations will be included in the by-patient data listings.

Concomitant Medications: All medications will be coded using the most current World Health Organization Drug Dictionary. Concomitant medications will be summarized by Anatomical Therapeutic Chemical Class and preferred term.

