19.7 Appendix 7: Sampson's Criteria of Anaphylaxis

ANAPHYLAXIS: Sampson's definition of anaphylaxis (clinical definition) is the acute onset of illness (minutes to several hours) which involves **SKIN, MUCOSAL TISSUE, or BOTH** (e.g., generalized hives, pruritus or flushing, swollen lips-tongue uvula) **with 1 OR more of the following (Sampson, 2006):**

- **RESPIRATORY:** Airway compromise (e.g., dyspnea, wheeze, or bronchospasm, stridor, reduced PEF, hypoxemia)
- **CIRCULATORY:** Reduced blood pressure or associated symptoms of end-organ dysfunction (e.g., hypotonia, syncope)

OR

2 or MORE of the following that occur rapidly after exposure:

- **SKIN, MUCOSAL TISSUE:** e.g., generalized hives, itch-flush, swollen lips-tongue-uvula
- **RESPIRATORY:** Airway compromise (e.g., dyspnea, wheeze, or bronchospasm, stridor and reduced PEF)
- **CIRCULATORY:** Reduced blood pressure or associated symptoms of end-organ dysfunction (e.g., hypotonia, syncope)
- **GASTROINTESTINAL:** Persistent gastrointestinal symptoms (e.g., Crampy abdominal pain, vomiting, nausea, diarrhea)

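### Section 13.4 does not exempt anaphylaxis from the single infusion-reaction term, so its incidence may not be readable from the planned safety tables

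*Combined protocol and SAP*

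**What the plan says.** Section 13.4 sets the recording rule. It covers "All AE considered by the Investigator" to be related to the infusion and "occurring within 24 hours of the start of the study drug infusion, should be captured as 1 AE", termed Infusion-Related Reaction. The components are kept: "All symptoms experienced by a patient during an IRR will be listed in the eCRF under 1 IRR". The one exception is for an individual symptom: "unless the Investigator believes a symptom is not part of the IRR, in which case it will be recorded separately".

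Section 13.3 lists the adverse events of special interest (AESI). One bullet reads "Infusion-related reactions and hypersensitivity reactions, including anaphylaxis", and every AESI must be flagged as such on the adverse event eCRF.

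Section 13.5 says that "all events of suspected anaphylaxis will be evaluated using" the Appendix 7 criteria. It does not say where the outcome of that evaluation is recorded or whether it changes the AE term. Section 11.4.8 adds histamine and tryptase sampling when anaphylaxis is suspected. Section 13.6.1 asks sites to report a diagnosis, where possible, when signs and symptoms have a common cause.

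Section 15.5 plans a count of patients with any AESI and a table of "TEAE of special interest by system organ class and preferred term". It plans no row or table for anaphylaxis or for Appendix 7-positive events.

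**The concern.** Long-term safety is part of the study objective (section 4), and section 2.3 reports IRR as the most common treatment-emergent event so far, mostly mild to moderate. An anaphylaxis recorded under that term would sit inside a large and mostly benign category. A reader of the AESI table could not tell whether an absent or small anaphylaxis row means few cases or means that cases were recorded as IRR.

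The protocol commits to judging suspected anaphylaxis by objective criteria, yet nothing carries that judgement into the data that are tabulated.

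**Working it through.** No arithmetic decides this point. The check sets the sections side by side.

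**1. Does the 13.4 symptom list overlap Appendix 7?** Every Appendix 7 category is represented in the list.

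| Appendix 7 category | Symptoms listed in 13.4 |
|---|---|
| Skin or mucosal | flushing, urticaria, pruritus |
| Respiratory | shortness of breath, bronchospasm |
| Circulatory | hypotension |
| Gastrointestinal | nausea, vomiting, abdominal pain |

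The first limb of Appendix 7 needs acute skin or mucosal involvement plus a respiratory or circulatory feature. The respiratory feature is defined as "Airway compromise (e.g., dyspnea, wheeze, or bronchospasm, stridor, reduced PEF, hypoxemia"). The second limb needs any two of the four categories soon after exposure. Acute urticaria with bronchospasm during an infusion is therefore both a 13.4 reaction and Appendix 7-positive. Appendix 3 grades IRR from 1 to 5, so severity does not take an event out of the term.

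**2. Does any section take such an event out of the 13.4 rule?**
- The exception in 13.4 concerns a symptom that the Investigator thinks is not part of the reaction. In an anaphylactic reaction to the infusion, the symptoms are part of it.
- 13.3 names IRR and anaphylaxis together and does not say which term prevails.
- 13.5 requires an evaluation but no term, field or table.
- 13.6.1 favors a diagnosis but does not mention 13.4.

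**3. Where does the event appear under each reading?** I assume that the MedDRA term follows the recorded AE term.

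| Output in 15.5 | Site records IRR (13.4) | Site records anaphylaxis (13.6.1) |
|---|---|---|
| TEAE and maximum-severity tables | yes, as IRR | yes, as anaphylaxis |
| Count of patients with any AESI | yes | yes |
| AESI table by preferred term | IRR row | anaphylaxis row |
| Serious TEAE table, if serious | yes, as IRR | yes, as anaphylaxis |
| Listings | yes | yes |

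Both sites have followed the protocol. The anaphylaxis row then counts only the events that sites chose to term that way, plus events outside the 13.4 rule (onset after 24 hours, or not judged infusion-related).

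**4. Can the cases be recovered afterwards?** Only in part. The symptoms are on the eCRF, but for timing 13.4 mentions only the start of the first symptom and the end of the last. Appendix 7 also depends on how quickly features appear and whether gastrointestinal symptoms persist. No such search is planned in the text.

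**5. Illustration only.** If 183 patients were treated and none were shown with anaphylaxis, the exact upper 95% limits would be:
- one-sided: 1 − 0.05^(1/183) = 1.62%
- two-sided: 1 − 0.025^(1/183) = 2.00%

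A reader who computed such a limit would be misled if one or more Appendix 7-positive events lay in the IRR row. These figures do not measure the defect: 183 is an enrollment ceiling (section 15.1), and section 15 plans no formal inference.

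**The case against.** The strongest reply is that little is hidden. IRR is itself an AESI and must be flagged, so the event stays in every relevant table and in the listings, with its symptoms on the eCRF. If serious, it is also reported as an SAE within 24 hours (section 13.7.4). That stands. A reader might infer that anaphylaxis would disappear from the AE and AESI tables, and the documents do not support this. What can be lost is its separate identification.

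The second reply is that sites have good grounds to record anaphylaxis as a diagnosis. It is a named AESI with its own section, criteria and laboratory work-up, and 13.6.1 prefers diagnoses. The 13.4 rule also depends on the Investigator's judgement of relatedness. This also stands in part: misrecording is possible, not certain. But it does not settle the matter, because 13.4 is the specific rule for these events and sites that resolve the conflict differently produce a count that cannot be interpreted.

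The third reply is that section 15 refers full detail to a separate Statistical Analysis Plan, which is not in the text reviewed and may add a summary. That cannot be excluded. Such a summary would still need an Appendix 7 result in the database, and the protocol does not say that one is captured.

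**Conclusion.** The point holds as a recording conflict with a direct effect on reporting. For an infusion-related anaphylaxis within 24 hours, 13.4 read literally gives one term (IRR), 13.6.1 points to another, and neither 13.5 nor 15.5 resolves it. Anaphylaxis incidence therefore cannot be read reliably from the planned tables, whether the anaphylaxis row shows zero or some other number.

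The effect is confined to identification and to consistency across sites. Total TEAE, AESI and serious-event counts of patients are not shown to be wrong. The number of affected events cannot be estimated from the documents. The conclusion assumes that coding follows the recorded term and that no document outside the reviewed text already supplies an Appendix 7 field and summary. It is worth correcting because safety is central to the study and the correction is small.

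**What to change.** Reconcile sections 13.3, 13.4, 13.5 and 13.6.1 with one statement: a suspected anaphylaxis that is evaluated under 13.5 and found to meet Appendix 7 is recorded under its own AE term, or carries an explicit Appendix 7-positive flag on the AE eCRF, and is not identified only as IRR.

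Keep the 13.5 condition that the event was suspected to be anaphylaxis. Without it, the second limb of Appendix 7 could turn an ordinary reaction with flushing and persistent nausea into anaphylaxis and push the count upward. Section 2.3 lists flushing and nausea among the common IRR symptoms.

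Add to section 15.5, and to the separate analysis plan, one summary of the number and percentage of patients with Appendix 7-positive events, shown apart from other IRRs.

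The cost is one term rule or eCRF field and one extra table. Section 13.5 already requires the evaluation, so no new assessment of patients is needed and treatment is unaffected.
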